**aEscape at W12:**

**Placebo, 22.5 mg, 45 mg, 90 mg or 135 mg.** Subjects that fail to achieve EULAR good or moderate response at W12, escalate to 180 mg (or the highest remaining dose) for remainder of study from W14

**bEscape at W24:**

**Placebo, 22.5 mg, 45 mg, 90 mg or 135 mg.** Subjects that remained on their original randomised dose, with DAS28 >3.2 at W24, escalate to 180 mg (or the highest remaining dose) for remainder of study from W26

**cMandatory withdrawal point:**

Any subject not achieving EULAR good/moderate response at W36 will be withdrawn from the study at W38

Study visits:

Screening assessments (Visit 1) will be performed up to 28 days prior to the baseline visit (Visit 2) on Day 1 (start of study treatment). Subsequent visits are planned on Days 3, 8, 15, 22, 29 (=Week 4) and then every other week (EOW) in weeks 6 through 52, with a follow-up visit in Week 62. Subjects who discontinue the study treatment should have an early withdrawal visit with a subsequent follow-up visit  $\geq$ 12 weeks after the last dose of study treatment. The exact timing of each assessment is listed in the Time and Events Table in section [3.1.2](#).

### 3.1.2 Time and Events Table (Combination Treatment with GSK3196165 and MTX)

**Table 1 Time and Events Table**

Procedures	Screening - up to 4 weeks	Baseline	Treatment Period																												FU	EW 1		
			Week																															
		Visit	Visit																															
		1	2	3	4	5	6	7	8	9	10	11	12	13	14	15	16	17	18	19	20	21	22	23	24	25	26	27	28	29	30	31	32	
		Day	Day	Day 																														
		-7	1	3*	8	15	22	29	43	57	71	85	99	113	127	141	155	169	183	197	211	225	239	253	267	281	295	309	323	337	351	365	435	
Written Informed Consent(s)	X																																	
Subject Demography	X																																	
Medical, Disease, Therapy History	X																																	
Inclusion/Exclusion Criteria	X																																	
Efficacy and PRO Assessments																																		
Swollen (66) & Tender (68) Joint Count 	X		X 		X	X		X	X	X		X		X		X		X		X		X		X		X		X		X	X	X		
Patient's Assessment of Arthritis Pain, Patient's Global Assessment of Arthritis, Physician's Global Assessment of Arthritis 	X		X 		X	X		X	X	X		X		X		X		X		X		X		X		X		X		X	X	X		
HAQ-DI 	X		X 		X	X		X	X	X		X		X		X		X		X		X		X		X		X		X	X	X		
BFI Question 3, FACIT-Fatigue, SF-36 (acute v2) 			X 					X				X				X				X				X								X	X	X
RA Symptom and Impact Diary 			X 		X							X				X				X				X								X	X	X

Procedures	Screening - up to 4 weeks	Baseline	Treatment Period																												FU	EW 1					
			Week																																		
			1	2	3	4	6	8	10	12	14	16	18	20	22	24	26	28	30	32	34	36	38	40	42	44	46	48	50	52							
	Visit		Visit																																		
	1	2	3	4	5	6	7	8	9	10	11	12	13	14	15	16	17	18	19	20	21	22	23	24	25	26	27	28	29	30	31	32					
Day		Day		Day 																																	
-7		1		3*	8	15	22	29	43	57	71	85	99	113	127	141	155	169	183	197	211	225	239	253	267	281	295	309	323	337	351	365	435				
RA Symptom and Impact Diary, Actigraphy process 		X 		X 						X 	X 						X 	X 													X 	X 	X 				
Safety Evaluations																																					
Concomitant Medication	X		X 	Record all concomitant medications																																	
Physical Examination  , Vital Signs	X 		X	X	X	X	X	X	X	X	X	X	X	X	X	X	X	X	X	X	X	X	X	X	X	X	X	X	X	X	X	X					
12-lead ECG 	X																																	X	X		
AEs/SAEs/AESI	X		X	X	X	X	X	X	X	X	X	X	X	X	X	X	X	X	X	X	X	X	X	X	X	X	X	X	X	X	X	X	X				
Cough, Lung Auscultation, Pulse Oximetry, Borg Dyspnea Scale	X		X 	X	X	X	X	X	X	X	X	X	X	X	X	X	X	X	X	X	X	X	X	X	X	X	X	X	X	X	X	X	X				
Chest X-ray 	X																																				
Spirometry (FEV1, FVC)	X		X 																															X	X	X	
Dlco	X 		X 																															X	X	X	
Laboratory Assessments																																					
Hematology, Chemistry	X		X 			X	X	X	X	X	X	X	X	X	X	X	X	X	X	X	X	X	X	X	X	X	X	X	X	X	X	X	X				
Urinalysis (dip stick)	X						X	X	X	X	X	X	X	X	X	X	X	X	X	X	X	X	X	X	X	X	X	X	X	X	X	X	X				
Cholesterol, triglycerides, HDL, LDL 			X 																															X	X	X	
Pregnancy test 	S		U			U	U	U	U	U	U	U	U	U	U	U	U	U	U	U	U	U	U	U	U	U	U	U	U	U	U	U					
TB, HBsAg, Hep B cAb, HepC Ab, HIV	X																																				
RF, ACPA (anti-CCP)	X																																				

Procedures	Screening - up to 4 weeks	Baseline	Treatment Period																											FU	EW 1								
			Week																																				
			1	2	3	4	6	8	10	12	14	16	18	20	22	24	26	28	30	32	34	36	38	40	42	44	46	48	50	52									
	Visit	Visit																																					
		1	2	3	4	5	6	7	8	9	10	11	12	13	14	15	16	17	18	19	20	21	22	23	24	25	26	27	28	29	30	31	32						
	Day	Day	Day 																																				
	-7	1	3*	8	15	22	29	43	57	71	85	99	113	127	141	155	169	183	197	211	225	239	253	267	281	295	309	323	337	351	365	435							
CRP, ESR 	X	X 	X	X	X	X	X	X	X	X	X	X	X	X	X	X	X	X	X	X	X	X	X	X	X	X	X	X	X	X	X	X							
Other Laboratory Assessments			X 	X*	X	X		X	X	X	X	X	X	X	X	X	X	X	X	X	X	X	X	X	X	X	X	X	X	X	X	X							
PK Sampling (GSK3196165) 			X 	X*	X	X		X	X	X	X	X	X	X	X	X	X	X	X	X	X	X	X	X	X	X	X	X	X	X	X	X							
GM-CSF & PD blood biomarkers			X 	X*	X	X		X	X	X							X				X												X	X	X				
PGx sampling RNA 			X 								X						X				X													X	X	X			
PGx sampling DNA 			X 																																				
Lung biomarkers 			X 								X						X				X														X	X	X		
Cholesterol/4β-hydroxycholesterol			X 								X																												
Immunogenicity 			X 			X		X			X						X				X														X	X	X		
Anti-GM-CSF auto-antibodies 			X 																																				
Study Treatment			X	X	X	X	X	X	X	X	X	X	X	X	X	X	X	X	X	X	X	X	X	X	X	X	X	X	X	X	X	X	X	X					
GSK3196165/placebo (Methotrexate and folic acid weekly throughout treatment with GSK3196165)			X	X	X	X	X	X	X	X	X	X	X	X	X	X	X	X	X	X	X	X	X	X	X	X	X	X	X	X	X	X	X	X					
Rescue point for possible dose escalation											X						X																						
Decision point for mandated withdrawal 																											X												

1. All subjects who discontinue study medication prematurely should have an early withdrawal (EW) visit as soon as possible after study agent discontinuation and then return for a follow-up safety visit at least 12 weeks after last dose of study medication.
2. The same individual (where possible) should perform all disease assessments for an individual subject (with separate joint assessor).
3. All PRO assessments should be conducted before any tests, procedures, assessments or consultations, to avoid influencing the subjects' perception.
4. Assessments may be performed up to 24 hours before dosing GSK3196165.
5. Non-actigraphy sub-study subjects only.
6. Performed in a subset of consenting subjects only.
7. Actigraphy device placed and tagging process started (as detailed in the SRM), RA Symptom and Impact Diary questionnaire started on the same day at home using an electronic PRO (ePRO) device and completed on a daily basis until next visit.
8. Actigraphy device collected and RA Symptom and Impact Diary questionnaire completed at site visit and ePRO device collected.
9. All safety evaluations should be conducted before dosing GSK3196165.
10. Complete physical at baseline, and then limited physical examination (abdominal examination and heart sounds) thereafter.
11. ECG should be performed before vital signs, blood draws, and dosing.
12. Unless performed within previous 12 weeks (No need to repeat if subject re-screened).
13. Chest HRCT if  $D_{LCO} \geq 60\% - <70\%$  predicted (No need to repeat if subject re-screened).
14. If the screening  $D_{LCO}$  value is  $\geq 70\%$  predicted, but the subsequent "Day 1" value is  $<70$  but  $\geq 60\%$  predicted, the  $D_{LCO}$  test must be repeated if still within the screening window. If the repeat value is  $\geq 70\%$ , the "Day 1" activities may be completed, but if the value is again  $<70\%$ , dosing must be postponed and a chest HRCT performed. If this cannot be done within the screening window then the subject must be re-screened.
15.  $>8h$  fasting required before blood draw.
16. For women of child-bearing potential. S=serum; U=urine.
17. ESR measured locally.
18. Blood samples taken before dosing GSK3196165.
19. In consenting subjects.
20. To be analysed at end of study or in event of pulmonary safety signal.
21. In addition to these scheduled immunogenicity assessments, "event-driven" testing will also be employed for those subjects that experience anaphylaxis, serious hypersensitivity, or adverse events related to study drug administration that led to withdrawal from the study.
22. GSK3196165 or placebo must be administered on the same day each week  $\pm 1$  day for the first 5 weekly doses, thereafter on the same day EOW  $\pm 3$  days.
23. Any subject not achieving EULAR good/moderate response at Week 36 will be withdrawn from the study at Week 38.

\* The Day 3 blood sample may be drawn  $\pm 1$  day.

### 3.1.3 Treatment Arms and Duration

In the “dose selection” component of the study, subjects will be randomised (1:1:1:1:1) to placebo or one of five subcutaneous GSK3196165 doses, in combination with MTX (at a dose between 15-25 mg previously received for at least 12 weeks, with a stable and tolerated dose and route of administration for  $\geq 4$  weeks).

Treatment with GSK3196165 will be given as a single subcutaneous (SC) injection by an unblinded administrator (shielded to subjects) weekly for 5 injections (Days 1, 8, 15, 22, 29), then EOW thereafter beginning at Day 43 (Week 6).

GSK3196165/placebo must be administered on the same day each week  $\pm 1$  day for the first 5 weekly doses. Following this GSK3196165/placebo must be administered on the same day EOW  $\pm 3$  days.

After the Day 85 (Week 12) administration:

- “Escape therapy” is provided for all subjects not on the 180 mg dose:
  - Subjects in the placebo, 22.5 mg, 45 mg, 90 mg and 135 mg arms will be escalated in a double-blind fashion to the 180 mg (or the highest remaining) dose at Week 14 if they have failed to achieve European League against Rheumatism (EULAR) good/moderate response (see section 3.2.1) at Week 12.
  - Subjects in these groups who do not meet this criterion and therefore do not escalate therapy at Week 14 have another opportunity for “escape” at Week 24 with escalation in a double-blind fashion to the 180 mg (or the highest remaining) dose at Week 26 if their DAS28(CRP) score at this timepoint is  $>3.2$ .

This escape requirement is based on EULAR guidance and a review of response to MTX in randomised clinical studies.

Any subject that does not achieve EULAR good/moderate response at Week 36 will not be dosed at Week 38, and will be withdrawn from the study.

### 3.1.4 Study Oversight and Dose Selection

A Data Review Committee (DRC) consisting of external rheumatology, infectious disease and respiratory experts, and GSK study team members that have no involvement in the acquisition of the data or direct contact with sites, will review ongoing unblinded safety data from the study and unblinded efficacy data at the interim analyses.

Pharmacokinetic (PK) concentration time data will be presented to DRC only if required to aid the interpretation of the efficacy or safety data.

The first DRC review of safety data will be conducted after approximately 10 subjects per arm have completed 5 weeks of treatment, and subsequent reviews will take place approximately every 12 weeks thereafter until the end of the study. The recommendation to stop the study or randomisation to specific arms will be made by the DRC and ratified by the GSK steering committee consisting of senior GlaxoSmithKline Pharmaceuticals, R&D leaders.

Interim analyses will be performed to assess futility and the dose-efficacy relationship when 90 subjects have completed 4 and 12 weeks of treatment. If the recruitment rates allow, these

interim analyses will be aligned with safety reviews to allow an assessment of benefit versus risk. Based on these interim analyses, the overall efficacy and the dose-response model will be defined and the effective therapeutic dose(s) of GSK3196165 selected. New subjects will be randomised to the dose(s) identified, which will be from the dose range already studied, with the maximum dose not exceeding 180 mg. If there is no evidence of efficacy, the study could also be stopped for futility.

There will be no pause in recruitment whilst the review of safety data or interim analyses is conducted.

Once the effective therapeutic dose(s) have been selected at the interim analyses, treatment allocation could be adapted so that randomisation is stopped to the ineffective doses and future subjects are randomised to only the effective dose(s) and placebo. Subjects already in the study will remain on the arm to which they were randomised. There is a rescue option for all subjects, whereby the subjects can be escalated to the highest remaining dose for the remainder of the study. The randomisation ratio will be 1:1:1:1:1:1 across the original 6 arms of the study (*i.e.*, n=35 in each dosing group). However, due to the re-allocation of subjects once the effective dose(s) are known, it is likely that at the end of the study there will be more subjects in the effective dose groups and placebo.

Medical monitoring will happen in the form of monthly blinded data review meetings which include but are not limited to:

- Medical review of protocol deviations
- Medical review of high panic lab alerts
- Cumulative data review (includes summaries of reason for screening failures, disposition, adverse events, serious adverse events, disease related events and chest x-rays)
- Medical review of coding

Further information on the medical monitoring can be found in the Medical Data Review Plan (MDRP) and the Medical Monitoring Plan (MMP).

The primary analysis will occur 24 weeks after the last subject was randomised. The final analysis will occur after the end of the study which is defined as the last subject's last visit.

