#### **4.9.1.3 Adjustments for Covariates**

Adjustment for the following covariates will be considered: baseline value, disease duration (<2 years,  $\geq$ =2 years), weight, age, and sex.

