#### **4.9.1.4 Multiple Comparisons/Multiplicity**

For this phase II study no adjustment for multiple testing is planned.

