## 4.9.2 Key Efficacy Analyses

### 4.9.2.1 Interim Analyses

The outputs listed in [Table 5](#) will be produced at the efficacy interims. All data will be summarised using the Intent-to-Treat population.

The second interim analysis may allow an assessment of subjects with early RA (<2 years disease duration). Results may impact the proportion of subjects randomised to this subgroup.

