For binary endpoints with repeated measures over time, Generalized Estimating Equations (GEE) methodology will be used to take correlation among subject-level responses over time into account. The model will include data from all assessment points from Week 1 to Week 62. Due to only few expected subjects with remission in some randomised treatment groups (especially placebo) only standard errors and resulting confidence intervals will be adjusted. To this end an independent working correlation structure will be assumed and standard errors will be calculated based on the empirical sandwich covariance estimate (default setting for PROC GENMOD in SAS) (Stokes, Davis, & Koch, 2012).

For the primary analysis of DAS28(CRP) remission at Week 24, the GEE model will include terms for randomised treatment group, baseline DAS28(CRP), visit and interaction terms for treatment group-by-visit and baseline-by-visit. A sensitivity analysis including covariates age, gender, weight and disease duration (<2 years,  $\geq 2$  years) will be considered by adding covariate terms to the repeated measures model one at a time along with the covariate-by-treatment group interaction term. If the interaction term is not significant at  $\alpha=0.10$  it will be removed from the model. Likewise, if the covariate term is not significant at  $\alpha=0.10$  it will be removed from the model. Other covariates will be tested in a similar manner.

Survival analyses (time to event analyses) will be conducted for the final analysis using Kaplan-Meier methods, comparing each GSK3196165 dose to placebo. Between-group differences will be analysed using the log-rank statistic. Median time to remission will be presented for each randomised treatment group. Kaplan-Meier plots of the time to remission will be presented. Subjects who withdraw from the study are censored at the time of withdrawal. All other subjects are censored at the end of the study.

In addition to summaries of the individual components of composite endpoints, numbers and percentages of subjects meeting the following criteria will be presented:

- TJC68  $\leq 1$
- SJC66  $\leq 1$
- CRP  $\leq 1\text{mg/dl}$
- PtGA  $\leq 10$
- SDAI  $\leq 3.3$

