#### **4.13.1 Primary Analysis**

The sample size for the primary analysis and hence the overall sample size for the study is based on detecting a 30% difference from placebo in the proportion of subjects in remission (DAS28 score <2.6) at Week 24 of the 52 week double-blind treatment period for each GSK3196165 dose.

Using a Fisher's exact test, a sample size of 35 subjects per arm will provide approximately 90% power to detect a difference of 30% in the proportion of subjects in remission between each GSK3196165 dose (33%) and placebo (3%) at the two-sided  $\alpha=0.05$  level at 24 weeks. The placebo rate of 3% is based on a literature review of current therapies presenting DAS28(CRP) remission results. No adjustments will be made to the sample size to account for the multiple doses in this Phase 2 study.

The least significant difference this sample size will detect is an approximate 17% difference from placebo.

The sample size will not be increased to account for dropouts and all dropouts within the treatment period will be classed as non-remitters for the primary analysis.

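### If Interim 2 drops a dose, that dose's comparison with placebo becomes partly non-concurrent, and no planned model has an enrolment-stage term

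*SAP*

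**What the plan says.** SAP 3.1.4 (and Protocol 4.3) says that, once effective doses are identified, allocation could be changed so that "randomisation is stopped to the ineffective doses and future subjects are randomised to only the effective dose(s) and placebo". SAP Table 4 gives the arm-dropping rule at Interim 2 only: a dose is a candidate if its modelled Week 12 difference from placebo is above -1.0. Recruitment does not pause during the interim analyses, and Protocol 9.2.3 keeps the maximum study size fixed. The ratio after the change is not stated.

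Interim 2 may also look at subjects with early RA: "Results may impact the proportion of subjects randomised to this subgroup" (SAP 4.9.2.1). SAP 3.1.1 says these subjects may gain more from treatment.

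On analysis:

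- SAP 4.3 analyses all endpoints in the ITT population by randomised group, and SAP 4.9.2.2 compares each dose with placebo. Nothing restricts a dropped dose to concurrently randomised placebo.
- For the primary endpoint, "the GEE model will include terms for randomised treatment group, baseline DAS28(CRP), visit and interaction terms for treatment group-by-visit and baseline-by-visit".
- The MMRM follows the interim specification: treatment, visit, their interaction and baseline.
- The Week 24 dose-response model is fitted without covariates.
- SAP 4.9.1.3 reads "Adjustment for the following covariates will be considered: baseline value, disease duration", followed by weight, age and sex. Enrolment stage and calendar time are not listed.
- Disease duration is a sensitivity covariate in the GEE, removed if not significant at 0.10. It is also a planned subgroup factor (SAP 4.9.1.6, Table 6), and SAP 4.9.2.2 adds subgroup-by-treatment analyses.

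**The concern.** When an arm closes, its subjects all come from the first enrolment stage, whereas placebo continues to recruit. Pooling all placebo then sets first-stage treated subjects partly against second-stage controls. Any difference in outcome between stages, whether from case mix, sites or background care, enters the estimated effect of the dropped dose. Here the same interim look can also revise the early-RA share, so the plan allows a change of population at the moment allocation changes.

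The dose-response curve has the same exposure. Its dropped doses would be fitted to one stage, and placebo and the retained doses to both. The study exists to choose Phase 3 doses, so the shape of the curve at the lower doses matters even when those doses have been closed.

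**Working it through.** **The plan's own power figure.** Exact enumeration of the two-sided Fisher test at 35 per arm, 3% against 33%, gives 90.9%; SAP 4.13.1 states about 90%. The figure is right, but it does not describe a dropped arm, which stops short of 35.

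**Which doses the rule would drop.** From the assumed Week 12 changes in SAP 4.13.2:

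- 22.5 mg: -1.54 - (-1.0) = -0.54
- 45 mg: -1.83 - (-1.0) = -0.83
- 90 mg: -2.10 - (-1.0) = -1.10

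Against the -1.0 threshold, 22.5 and 45 mg are expected to meet the dropping rule and 90 mg and above are not. That is the scenario used below.

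**Second-stage share of placebo.** The documents give no accrual rate, so N, the number randomised before the change, is assumed to be 120, 150 or 180. Allocation is equal over six arms before the change and assumed equal over four (placebo and three doses) after it:

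s1 = N/6; s2 = (210 - N)/4; share w = s2/(s1 + s2)

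**Bias in the raw difference, dropped dose minus placebo.** If second-stage outcomes shift by d in every arm, the size of the bias is w × d. Here d = 0.3 DAS28 units is an assumption.

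| N before change | s1 | s2 | w | bias at d = 0.3 |
|---|---|---|---|---|
| 120 | 20 | 22.5 | 53% | 0.16 |
| 150 | 25 | 15 | 38% | 0.11 |
| 180 | 30 | 7.5 | 20% | 0.06 |

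With only one dose kept and N = 120, s2 = 90/2 = 45 and w = 45/65 = 69%.

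**Dose-response curve.** A three-parameter Emax model was fitted to the plan's assumed means, weighted by n per arm, with ±d × w added to placebo and retained doses. The Week 12 means stand in for Week 24, for which the plan gives none. Without a shift, the fitted effect at 22.5 mg is -0.55.

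| N before change | d | fitted effect at 22.5 mg |
|---|---|---|
| 120 | 0.3 | -0.45 to -0.69 |
| 150 | 0.3 | -0.47 to -0.65 |
| 180 | 0.3 | -0.50 to -0.60 |
| 120 | 0.1 | -0.51 to -0.59 |

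The weaker estimate arises when second-stage subjects improve more, the stronger when they improve less. The retained doses move by at most about 0.05.

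**Remission scale.** With N = 120 and w = 0.53, a placebo rate moving from 3% to 10% (two of the rates in the plan's power table) biases the raw difference for a dropped dose by 0.53 × 7 = 3.7 points. For the early-RA route alone, assume a 20-point change in share and a 10-point remission gap between early and established RA on placebo. Placebo remission then moves by 2 points and the bias is 0.53 × 2 = 1.1 points.

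**Power with concurrent placebo only.** For 3% against 33%, the exact Fisher test gives 65% at 20 vs 20 and 76% at 25 vs 25. Pooling all placebo with 20 in the dropped arm and no drift gives 89% if two doses are kept and 94% if one is kept. With 20 concurrent placebo subjects at 3%, 0.6 remitters are expected, and the chance of none is 0.97^20 = 54%.

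**The case against.** The strongest reply is that the problem is conditional and may be small. Allocation may never change, and if no dose is dropped there is no confounding. Recruitment continues while 90 subjects reach Week 12, so the number randomised before the change could be well above 120. Nothing in the documents supports a shift of 0.3, and at N = 120 with SD 1 the sampling standard error of the fitted 22.5 mg effect is about 0.20, larger than the worst bias shown. All of this stands, and it limits the size of the point. The structural gap remains, because the plan expects low doses to be closed and has nothing in place if outcomes then differ by stage.

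A second reply is that the SAP already deals with early RA. This is partly right: the disease-duration subgroup and interaction analyses examine that shift. They do not cover other drift, and they leave the primary GEE and the Week 24 curve unadjusted. The plan's expectation for early RA is also a larger treatment effect, which would move the retained doses and need not move placebo. A common 0.3 shift should therefore not be read as the predicted result of changing the early-RA share.

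A reader might infer more than the documents support:

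- **That dropped doses lose their randomised control.** First-stage placebo was randomised alongside them and stays in the pool.
- **That retained doses are biased as well.** With an unchanged ratio to placebo, stage is balanced between them. The new ratio is not stated, so this should be settled.
- **That dose selection at Interim 2 is distorted.** That Week 12 fit precedes any allocation change and is fully concurrent.

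**Conclusion.** The point holds in conditional form. If Interim 2 drops a dose, its comparison with placebo in the GEE and MMRM is partly non-concurrent, and the Week 24 dose-response curve mixes one-stage and two-stage arms without adjustment. Under the stated assumptions the raw bias is 0.06 to 0.16 DAS28 units for a 0.3-unit stage shift, and the fitted 22.5 mg effect moves from -0.55 to between -0.45 and -0.69 in the worst case shown. A 0.1-unit shift does much less.

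The absence of a stage term is certain from the text. The size of any stage effect, the number randomised before the change and the ratio afterwards are not given, so the magnitudes are illustrations rather than forecasts. The point does not call into question the primary comparison for retained doses at an unchanged ratio. It is a worthwhile and inexpensive repair to the SAP.

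**What to change.** Before the Week 24 unblinding, state the allocation ratio that applies after any change and add text that takes effect only if an arm is dropped:

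1. Add a two-level factor for randomisation before or after the allocation change, with its visit interaction, to the GEE and the MMRM. The interaction is needed because the treatment and baseline terms in the GEE also vary by visit, and a single constant shift might not adjust Week 24.
2. Let E0 in the Week 24 dose-response model differ by stage.
3. As a sensitivity analysis, fit stage-by-treatment for the retained doses. The additive factor assumes a common shift and cannot capture a treatment effect that differs by stage; for dropped doses that difference cannot be estimated.
4. As a supportive analysis, compare each dropped dose with concurrently randomised placebo only.

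Items 1 and 2 use the randomisation date and cost a few degrees of freedom and a small loss of precision for the dropped doses. Item 4 costs more: power falls to about 65% at 20 vs 20, with very few placebo remitters. It should therefore support the stage-adjusted model rather than replace it.
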